We have also used the PROMISE study findings to determine the required sample size for reporting other clinically relevant adverse events such as maternal and infant bone mineral content. In the P1084s study, a substudy of PROMISE mothers, the lumbar spine BMD declined significantly more through week 74 in the maternal TDF-ART arm compared to the infant NVP arm; mean (95% CI) percent change -2.06% (-2.90, -1.23) versus +1.09% (0.11, 2.07), mean difference -3.16% (-4.44, -1.87) (p-value< 0.001). Similarly, hip BMD declined significantly more through week 74 in the maternal TDF-ART arm compared to the infant NVP arm; mean (95% CI) percent change -5.37% (-5.99, -4.76) versus -3.05% (-3.72, -2.38), mean difference of -2.33% (-3.23, -1.42) (p-value< 0.001). We would require 150 infants exposed to maternal PrEP (TDF/FTC) and 150 infants unexposed (control group) based on 80% power to detect a pair-wise difference of 4-5% in mean WB-BMC and 6-7% in mean LS-BMC.

PASS 12 sample size software (Hintze, J. (2013). PASS 12. NCSS, LLC. Kaysville, Utah, USA. www.ncss.com) was used to calculate the samples sizes for testing equivalence between the treatment and control groups (Blackwelder WC. "Proving the null hypothesis" in clinical trials. Controlled clinical trials. 1982 Dec 31;3(4):345-53). We assumed equal adverse events rates (proportions) across the two groups i.e. zero difference and a maximum D (difference) of 7.5% for equivalence of the two groups. The table below displays the sample sizes required to achieve a 80% power with $\alpha = 0.05$ to establish equivalency for various adverse birth outcome prevalences based on actual data from the same setting published recently (Moodley, Theron et al. "Improved Pregnancy Outcomes with Increasing Antiretroviral Coverage in South Africa." BMC Pregnancy and Childbirth 16 (2016): 35. PMC. Web. 3 Mar. 2016). Based on the largest observed adverse birth outcome prevalence for pre-term delivery yields the largest required sample size i.e. 421 per group or 842 in total based on the assumptions mentioned above.

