Based on current data (maternal adverse events, maternal and infant bone mineral content depletion), all other adverse birth outcomes and maternal and infant adverse events can be housed within this sample size and will have smaller D as the relative prevalence decreases toward 0 i.e. narrower equivalence zones. Assuming a loss to follow-up of 5%, we would need 442 women in each group (884 in both arms combined) for the two year time frame of the study.

Outcome	n/N	Prevalence	Required sample size in each group for proposed equivalence trial	Total required sample size for proposed equivalence trial
Pre-term	1096/5916	18.5%	421	842
LBW	651/5916	11.0%	274	548
Small for GA	429/5916	7.3%	189	378
VLBW	141/5916	2.4%	64	128
Stillbirth	130/5916	2.2%	58	116

Main endpoint 1: sample size for safety in pregnancy for birth outcomes Prevalence adverse birth outcomes among HIV-ve (in descending order)

Based on a non-inferiority trial design: A sample size of 421 in the treatment group and 421 in the control group (i.e. 842 in total) achieves 80% power to detect a non-inferiority margin difference between the group proportions of 0.075 or 7.5%. The reference group proportion (pre-term delivery birth outcome) is 0.185 or 18.5%. The treatment group proportion is assumed to be 0.26 or 26% under the null hypothesis of inferiority. The power was computed for the case when the actual treatment group proportion is 0.185 or 18.5%. The test statistic used is the two-sided Z test (unpooled). The significance level of the test was targeted at two-sided 0.05 or 5%.

Secondary Endpoint

PASS 12 sample size software (Hintze, J. (2013). PASS 12. NCSS, LLC. Kaysville, Utah, USA. www.ncss.com) was to calculate this sample size. In order to show a 50% reduction in HIV infections, with significance level of 0.05 or 5% and 80% power, we would need to observe 66 HIV infections in total (44 in control arm [cumulative incidence of 12.72%] and 22 in the intervention arm [cumulative incidence of 6.36%]). This assumes an HIV incidence of 3 per 100 person years during the 6 months of pregnancy and 6 per 100 person years during the 18 months of breastfeeding [9]. Based on these assumptions, we would require 334 subjects in group or 668 in total. Assuming a loss to follow-up of 10%, we would need to increase this to 346 women in each group (692 in both arms combined) for the two year time frame of the study.

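### 421 per arm is a non-inferiority sample size but is presented as giving 80% power for equivalence; equivalence power for preterm delivery is about 75%, and no deciding test is named

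*Combined protocol and SAP*

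**What the plan says.** Section 10.3 describes the same 421 per arm in two ways.

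- **As an equivalence size.** The calculation assumes "zero difference and a maximum D (difference) of 7.5% for equivalence of the two groups". The plan continues: "The table below displays the sample sizes required to achieve a 80% power", at alpha 0.05, "to establish equivalency for various adverse birth outcome prevalences based on actual data from the same setting published recently". It adds that the prevalence "for pre-term delivery yields the largest required sample size i.e. 421 per group or 842 in total". Both sample-size columns of the table are headed for an equivalence trial, for example "Required sample size in each group for proposed equivalence trial". For the other outcomes, the plan says they "will have smaller D as the relative prevalence decreases toward 0 i.e. narrower equivalence zones".
- **As a non-inferiority size.** Below the table, 421 per group "achieves 80% power to detect a non-inferiority margin difference between the group proportions of 0.075 or 7.5" percent. The null value is a single one, 26% on treatment against a reference of 18.5%. The statistic is an unpooled Z test, and "The significance level of the test was targeted at two-sided 0.05 or 5" percent. The Synopsis gives the same non-inferiority statement.

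Section 10.4 leaves full details to a later analysis plan but says that it does describe the analysis of the primary safety endpoint. It lists Fisher's exact test on adverse event counts, then TOST for equivalence, then a random-effects non-inferiority analysis of the primary endpoints. Intention-to-treat is the main analysis and per-protocol the sensitivity analysis. TOST is given no margin, no per-side alpha and no named endpoint, and no test is said to decide.

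**The concern.** At one margin and under zero true difference, one sample size cannot give 80% power both for a single-margin test at one-sided 0.025 and for a conventional two-margin test at 0.05 per side. If 421 is right for non-inferiority, the equivalence power is overstated for preterm delivery, the outcome that sets the size of the trial.

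The second issue is interpretation. The two tests can give opposite answers on the same data. A favourable result, with fewer preterm births on PrEP, can pass non-inferiority and miss the lower equivalence bound. A modest excess on PrEP can pass TOST at 0.05 per side and fail non-inferiority at one-sided 0.025. The trial is open label (section 10.1), and section 10.4 allows the detailed analysis plan to be written after enrolment has begun. The rule for which result counts should therefore be in the protocol.

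**Working it through.** **Inputs** (section 10.3; allocation from section 10.1): preterm rate p = 0.185 in both arms; margin D = 0.075; true difference 0; 1:1 allocation; two-sided 0.05 for non-inferiority, so one-sided 0.025 at the single margin; 80% power; 421 evaluable and 442 enrolled per arm. The per-side alpha of TOST is not given. I take 0.05 per side as the conventional reading and show 0.025 as a sensitivity reading.

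**1. Reproduce 421.** 2p(1−p) = 2 × 0.185 × 0.815 = 0.30155.

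n = (1.960 + 0.8416)² × 0.30155 / 0.075² = 420.8, so 421.

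This is the single-margin formula with beta not split. One-sided 0.05 would give 332, and TOST sizing would give the numbers in step 3. The low birth weight (274) and small-for-gestational-age (189) rows also match the single-margin formula exactly. The very low birth weight and stillbirth rows match it only roughly (64 printed against 66; 58 against 61, from the rounded rates).

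**2. Equivalence power for preterm delivery.** SE = √(0.30155/n). At n = 421, SE = 2.68 points and D/SE = 2.802.

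- Non-inferiority power = Φ(D/SE − 1.960) = Φ(0.842) = 80.0%.
- TOST power = 2Φ(D/SE − z) − 1. At 0.05 per side: 2Φ(2.802 − 1.645) − 1 = 75.3%. At 0.025 per side: 2Φ(0.842) − 1 = 60.0%.

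| Evaluable per arm | Non-inferiority, one-sided 0.025 | TOST, 0.05 per side | TOST, 0.025 per side |
|---|---|---|---|
| 421 | 80.0% | 75.3% | 60.0% |
| 442 | 81.9% | 78.0% | 63.8% |

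Exact binomial enumeration agrees: 80.1%, 75.5% and 60.3% at 421; 82.0%, 78.0% and 63.9% at 442.

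The step from 80.0% to 75.3% combines two changes, a second margin and a looser per-side alpha. At matched alpha, the second margin alone takes power from 80.0% to 60.0% (0.025) or from 87.6% to 75.3% (0.05).

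**3. Size needed for 80% TOST power.** n = (z + 1.2816)² × 0.30155 / 0.075².

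- 0.05 per side: 459.1, so 460 (exact power 80.2%).
- 0.025 per side: 563.3, so 564 (exact power 80.1%).

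**4. The other outcomes.** At 421 per arm and D fixed at 7.5 points, TOST power at 0.05 per side is 93% for low birth weight, 99% for small for gestational age and near 100% for very low birth weight and stillbirth. The plan promises smaller margins without stating them. The D at which 421 per arm gives 80% non-inferiority power is 2.8016 × SE: 6.04, 5.02, 2.96 and 2.83 points respectively. At those margins TOST power is again 75.3% for each, by construction.

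**5. How often the tests disagree.** Take n = 421, no true difference, and TOST at 0.05 per side. Non-inferiority passes when the observed difference (PrEP minus control) is below 7.5 − 1.960 × 2.68 = 2.3 points. TOST passes when it lies within ±(7.5 − 1.645 × 2.68) = ±3.1 points.

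- Below −3.1: non-inferiority passes and TOST fails. Probability Φ(−1.157) = 12%.
- Between +2.3 and +3.1: TOST passes and non-inferiority fails. Probability 87.6% − 80.0% = 8%.

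Together, about 20%. With TOST at 0.025 per side the second case cannot occur.

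**The case against.** The best defence is that the arithmetic behind 421 is correct and only a label is wrong. The Synopsis and two places in section 10.3 state non-inferiority, one with a full specification, and the power for the question of harm is right. In section 10.4 only the non-inferiority sentence is tied to the primary endpoints, and a later analysis plan is promised. The lower equivalence bound fails when PrEP does better, which is not a safety concern. The shortfall for the other outcomes rests on margins the plan does not state; at 7.5 points they have ample power.

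Most of this is fair, and it limits the weight of the point: the non-inferiority design stands, and nothing follows for the other outcomes until their margins are stated. It does not remove the error. Section 10.3 claims 80% power for equivalence, and no reading of alpha reaches that at 421 or 442 per arm. A later analysis plan would not correct that statement, and section 10.4 says it covers the primary safety analysis already. The disagreement is also not confined to harmless cases: an excess of 2.3 to 3.1 points on PrEP could be reported as equivalent although non-inferiority was not shown.

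**Conclusion.** The concern holds. The 80% power stated for equivalence is wrong for preterm delivery: it is about 75% at 0.05 per side and about 60% at 0.025 per side with 421 per arm. The 80% stated for non-inferiority is right. The figures rest on the plan's own assumptions (18.5% in both arms, a 7.5-point margin, no true difference); only the per-side alpha of TOST had to be assumed. Section 10.4 needs a named deciding test, because TOST at 0.05 per side and non-inferiority would conflict in about 20% of trials with no true effect. This should be fixed, but it does not undermine the non-inferiority design.

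**What to change.** Keep 421 evaluable per arm and change the wording.

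1. **Section 10.3.** Relabel the equivalence text and both table headings as non-inferiority, or state the equivalence power for preterm delivery as about 75% at 0.05 per side.
2. **Section 10.4.** Name the deciding test that matches the sample size. Suggested text: *Non-inferiority for preterm delivery is shown if the upper limit of the two-sided 95% confidence interval for the risk difference (Arm A minus Arm B) is below 7.5 percentage points, by intention-to-treat.* Per-protocol stays as the planned sensitivity analysis. Fisher's exact test and the random-effects model then become supportive.
3. **TOST.** Keep it as supportive, with its per-side alpha, its margin for each outcome and its actual power.

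This adds no visits or participants; the cost is a less favourable equivalence power. One detail: 442 × 0.95 = 419.9, so the plan's inflation (421 × 1.05 = 442) falls about one woman per arm short of 421, which is trivial for power.

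Alternatively, if equivalence is to decide, size for it in 10.3 and say so in 10.4: about 460 evaluable per arm at 0.05 per side, or 564 at 0.025. With the plan's inflation that is 460 × 1.05 = 483 or 564 × 1.05 = 592 enrolled per arm, 41 or 150 more than 442. Dividing by 0.95 instead gives 485 or 594.

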10.2 Outcome Measures

Main Outcome Measure:

 Renal Function estimated by Serum Creatinine Clearance, adverse pregnancy outcomes (e.g., stillbirth, preterm delivery at < 37 weeks gestation, low birth weight <2,500 grams, and congenital anomalies) and Bone Mineral Density among women

Bone Mineral Density and growth parameters in neonates and infants until cessation of breastfeeding.

Other Outcome Measures:

- Confirmed presence of HIV infection detected by HIV NAT positivity at scheduled 3 monthly visits until 18 months.
- Adherence -self reported use of study product and pill count
- Partners HIV status at enrollment confirmed by Two POC tests and Adherence measured at delivery and 18 months postdelivery
- Antiretroviral drug level in plasma as a marker of adherence.
- Presence of viral resistance mutations that have been selected by Truvada (K65R, M184V) in participants who acquire HIV infection
- Mother to child transmission-reactive NAT testing performed in children born to mothers who acquire HIV infection during pregnancy and post-delivery.

Behavioural Risk:

- Number of sexual partners with whom participant had unprotected intercourse during pregnancy and postnatally
- Number of protected and unprotected acts of intercourse during pregnancy and postnatally
- Sexually transmitted infections acquired during pregnancy
- Sexually transmitted infections acquired postnatally
- Facilitators and barriers to adherence.

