10.4 Analysis Plan

Full details of the proposed analyses will be described in a statistical analysis plan that will be developed once enrollment to the study begins and prior to the commencement of analyses. Hence, here we limit the description of the proposed analyses to those for the primary safety endpoint.

Analyses will use the principle of intention-to-treat (i.e., using the randomised treatment assignment, whether or not study drugs were actually taken) and will include all randomised participants. This is generally the more conservative approach for analysis of trial data. However, it has been proposed that the smaller differences commonly observed in intention-to-treat analysis have the opposite effect when testing equivalence or non-inferiority. Hence for sensitivity analysis purposes (and as a required by the FDA) we will also perform a per protocol data analysis for comparative purposes (Walker, E., & Nowacki, A. S. (2011). Understanding Equivalence and Noninferiority Testing. Journal of General Internal Medicine, 26(2), 192–196. http://doi.org/10.1007/s11606-010-1513-8).

HIV Prevention Pregnancy Post-delivery Version 1.0

Data will be processed and analyzed using Stata 13.0 (tataCorp. 2013. Stata Statistical Software: Release 13. College Station, TX: StataCorp LP.) and R 3.2.4 (R Core Team (2016). R: A language and environment for statistical computing. R

Foundation for Statistical Computing, Vienna, Austria. ISBN 3-900051-07-0, URL http://www.R-project.org/.).

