The primary objective is to compare the frequency and seriousness of adverse events in women receiving tenofovir/emtricitabine in pregnancy and their newborn as opposed to women not receiving tenofovir/emtricitabine during pregnancy and their newborn. The number of adverse events experienced during pregnancy and post-delivery will be summarized for each of the study arms. This will also be stratified by seriousness of the adverse event. The number of adverse events will be compared between the study arms using Fisher's Exact test. Furthermore we will use the most widely used approach to test equivalence, namely the two one-sided test (TOST) procedure (Schuirmann DJ. A comparison of the two one-sided tests procedure and the power approach for assessing equivalence of average bioavailability. J Pharmacokin Biopharm. 1987;15:657–680. doi: 10.1007/BF01068419). Furthermore we will also employ a hierarchical or random effects modeling approach for a non-inferiority analysis for the primary endpoints.

A secondary objective is to compare the number of incident HIV infections in women during pregnancy alone and thereafter during breastfeeding. The analysis will be stratified by levels of PrEP adherence, partner involvement, condom usage and relationship dynamics. The cumulative incidence and associated 95% confidence intervals will be calculated for each study arm. The number of incident events will be compared for statistical difference between the study arms using Fisher's Exact test.

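### 7.5 points is the only limit stated for any birth outcome: the smaller limits promised for rarer outcomes are never given, congenital anomalies have none, and no rule settles conflicting tests

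*Combined protocol and SAP*

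**What the plan says.** Section 10.3 (Sample Size Calculation) assumes equal event rates in the two arms and "a maximum D (difference) of 7.5% for equivalence of the two groups". It sizes the trial on preterm delivery, the commonest adverse birth outcome at 18.5%, which gives 421 per group. The hypothesis is written out for that outcome only: "The treatment group proportion is assumed to be 0.26 or 26% under the null hypothesis of inferiority".

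The text above the table says that the other outcomes fit within this sample size and "will have smaller D as the relative prevalence decreases toward 0 i.e. narrower equivalence zones". The table has columns for counts, prevalence and required sample size (preterm 421, low birth weight (LBW) 274, small for gestational age (SGA) 189, very low birth weight (VLBW) 64, stillbirth 58 per group). It has no column for D. The two other margins in 10.3, 2% and 4-7%, concern maternal chemistry and bone mineral density.

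Section 10.2 lists among the main outcomes "adverse pregnancy outcomes (e.g., stillbirth, preterm delivery at < 37 weeks gestation, low birth weight <2,500 grams, and congenital anomalies". Congenital anomalies do not appear in the 10.3 table.

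Section 10.4 (Analysis Plan) gives three analyses:
- "The number of adverse events will be compared between the study arms using Fisher's Exact test".
- "we will use the most widely used approach to test equivalence, namely the two one-sided test (TOST) procedure".
- "a hierarchical or random effects modeling approach for a non-inferiority analysis for the primary endpoints".

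It leaves full detail to a statistical analysis plan to be written after enrolment opens and before analysis. It also says "here we limit the description of the proposed analyses to those for the primary safety endpoint".

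**The concern.** TOST and a non-inferiority analysis each need a limit before they can be run. For preterm delivery the limit is clear. For the rarer outcomes the text says it will be smaller, gives no figure, and then prints sample sizes that correspond to 7.5 points. An analyst looking for a number for stillbirth finds only one.

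A limit of 7.5 points is modest against a rate of 18.5% but very wide against a rate near 2%. If it were used for stillbirth or VLBW, the trial could report equivalence for an outcome that had doubled or tripled. In some trials it could do so while Fisher's test showed significant harm, and the plan does not say which result would stand. This matters because the aim is to show safety in pregnancy. The trial is also open label, so a limit chosen after events accumulate is open to question.

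**Working it through.** **Inputs.** From 10.3: D = 7.5 points, true difference 0, two-sided 0.05 (z = 1.9600), 80% power (z = 0.8416), unpooled Z test, 421 per group and the table's prevalences. From 10.1: equal allocation.

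**Step 1: reproduce the table.** n = (1.9600 + 0.8416)² × 2p(1−p) / 0.075². For preterm delivery: 7.849 × 2 × 0.185 × 0.815 / 0.005625 = 420.8.

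| Outcome | p | n at D = 7.5 | Table n | D solved back from table n (points) |
|---|---|---|---|---|
| Preterm | 18.5% | 420.8 | 421 | 7.50 |
| LBW | 11.0% | 273.2 | 274 | 7.49 |
| SGA | 7.3% | 188.9 | 189 | 7.47 |
| VLBW | 2.4% | 65.4 | 64 | 7.55 |
| Stillbirth | 2.2% | 60.0 | 58 | 7.63 |

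The last column uses the unrounded rates n/N. Every row was computed at about 7.5 points and none at a smaller D. Other set-ups at 7.5 points do not give 421 for preterm delivery: one-sided 0.05 gives 332, and TOST at 5% per side gives 460.

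**Step 2: what 7.5 points would allow.** The rate at the limit is p + 7.5 points: LBW 18.5% (1.7-fold), SGA 14.8% (2.0-fold), VLBW 9.9% (4.1-fold), stillbirth 9.7% (4.4-fold).

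**Step 3: worst-case pass rates.** These come from exact binomial enumeration with 421 per arm and limit 7.5 points. A pass is either an upper 95% Wald bound below 7.5 points, or a 90% interval inside ±7.5 points (TOST).

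| Stillbirth, control 2.2% | Pass, 95% bound | Pass, TOST | Fisher p<0.05 for harm | Pass and Fisher harm (95% bound / TOST) |
|---|---|---|---|---|
| Doubling, 4.4% | 0.984 | 0.993 | 0.370 | 0.353 / 0.363 |
| Tripling, 6.6% | 0.598 | 0.70-0.71 | 0.861 | 0.459 / 0.56-0.57 |

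The small ranges for TOST reflect rounding of the critical value (1.645 or 1.6449). Under a doubling, 63% of trials pass with no significant Fisher result. A VLBW doubling (2.4% to 4.8%) passes 0.969 (95% bound) or 0.985 (TOST). A doubling of LBW to 22.0% lies beyond its limit of 18.5%, and a doubling of SGA to 14.6% lies almost at its limit of 14.8%, so neither would pass often.

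**Step 4: one example.** With 27 against 9 stillbirths of 421 each, the difference is 18/421 = 4.28 points, the 95% Wald interval is 1.56 to 6.99, and Fisher p = 0.0032. The interval lies inside 7.5 points and excludes zero.

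**Step 5: the limits that 421 per arm supports.** D = 2.8016 × √(2p(1−p)/421): preterm 7.50, LBW 6.04, SGA 5.02, VLBW 2.96, stillbirth 2.83 points. At 7.5, 6.0, 5.0, 3.0 and 2.8 points the exact power is 0.801, 0.795, 0.797, 0.805 and 0.792. With a stillbirth limit of 2.8 points (95% bound), a true doubling passes 0.081 of the time and a tripling 0.0013.

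**Step 6: congenital anomalies.** The plan gives no planning rate for this trial. If 2% is assumed, D = 2.8016 × √(2 × 0.02 × 0.98/421) = 2.7 points; if 3% is assumed, D = 3.3 points.

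**The case against.** A reader might infer that the plan accepts a stillbirth rate of 9.7% against 2.2%, or that it has chosen 7.5 points as the stillbirth margin. The documents do not support that. Section 10.3 calls 7.5 a maximum, says the other outcomes will have a smaller D, and writes out a 7.5-point hypothesis only for preterm delivery. The table can fairly be read as showing that rarer outcomes fit within 421 per group, not as fixing how they will be judged. The pass rates above therefore describe a worst-case reading.

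A reader might also infer that harm would be concealed. It would not be: Fisher's test is planned, and 27 against 9 would produce p = 0.003. But Fisher's test detects only 37% of true doublings of stillbirth, so it does not replace a suitable limit, and the plan does not say what to conclude when the two results conflict.

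Two further arguments carry some weight. The smaller limits can be derived from figures already in 10.3, and limits for individual outcomes could sit in the later analysis plan, which is not among the documents. Against that, 10.4 says the protocol itself covers the primary safety endpoint, and the later plan is to be written after enrolment has begun in an open-label trial. That supports stating the limits early. It does not show that a wrong margin was chosen.

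**Conclusion.** The point stands as an omission and an inconsistency that should be fixed. The text promises narrower limits, the table uses 7.5 points throughout, no other value is given for a birth outcome, congenital anomalies have none, and two of the three planned analyses cannot be run for the rarer outcomes as written.

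The consequence is conditional. If the only stated limit were used, with control rates as in the table and 421 evaluable women per arm, a stillbirth doubling would pass 98 to 99% of the time and a tripling about 60 to 70%. Under a tripling, about 46 to 56% of trials would pass and also show significant harm. The practical weight falls on stillbirth, VLBW and congenital anomalies. Nothing here questions the preterm limit of 7.5 points or the sample size.

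**What to change.** 1. State that 7.5 points is the limit for preterm delivery only, and relabel the existing sample-size column 'n at D = 7.5'.
2. Add a D column based on the test that 10.3 states (unpooled Z, two-sided 0.05, 80% power, 421 per group): preterm 7.5, LBW 6.0, SGA 5.0, VLBW 3.0, stillbirth 2.8 points. If TOST at 5% per side is kept, leave preterm at 7.5 points, accept the lower power (0.755 by exact enumeration), and do not widen the limit.
3. Say that these are precision limits set by the sample size, not clinically justified margins: 2.8 points still allows stillbirth of 5.0% against 2.2%, a 2.3-fold rate. For any outcome without a clinically justified limit, including congenital anomalies, report the difference with its interval and make no equivalence claim. An anomaly row is optional and must state its assumed rate (about 2.7 to 3.3 points for 2% to 3%).
4. State that an outcome whose 95% interval excludes zero in the harmful direction is reported as an increase, even if the interval lies inside the margin.

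Make these changes before outcome data accumulate. The cost is protocol and analysis-plan wording and one table column, with no extra participants. The downside is that a safety claim becomes harder to reach for rare outcomes.

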7.17 Participant Retention

The target retention rate will be 90% per annum. During the informed consent process the participant will be informed of the planned retention procedures. This is to ensure participant awareness of all the efforts that will be undertaken to contact them in the event that they miss a scheduled study visit throughout the participant's Involvement in the study (up to 2 years for those who enroll early in pregnancy). Study participants will be informed that staff will attempt to make telephonic contact with them for missed visits or for unscheduled visits if the need arises, failing which home visits will be made. The Protocol Team will track retention rates. Once a participant is enrolled in the study, study staff will make every reasonable effort to ensure adequate locator information is available for follow-up tracking. A missed visit in either arm will prompt a single telephonic reminder, where the participant is spoken to directly and reminded of her clinic visit. A home visit will be triggered if a second clinic visit is missed. A home visit will be considered complete when the participant is met in person. A maximum of 3 attempts will be made to complete a home visit. Retention efforts will be conducted by the same team for both arms.

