10.3 Sample Size Calculation

In view of the limited evidence of safety data from studies of PrEP (TDF/FTC) use in pregnancy, we based our sample size on data provided in studies of ART treatment in HIV infected pregnant women. In few studies, comparisons were made to HIV uninfected pregnant women.

To compare the frequency and seriousness of adverse events in women receiving tenofovir/emtricitabine in pregnancy as opposed to women not receiving tenofovir/emtricitabine in pregnancy, we have based our sample size on the main clinically relevant pregnancy outcome.

Adverse Pregnancy Outcomes

Although all pregnancy outcomes will be compared between the intervention (immediate PrEP) and control (deferred PrEP) groups, we based our sample size on the expected preterm delivery proportion among HIV uninfected women (South Africa 18.5%, Botswana 19%). A sample size of 421 in the Immediate PrEP group and 421 in the Deferred PrEP group (i.e. 842 in total) achieves 80% power to detect a non-inferiority margin difference between the group proportions of 0.075 or 7.5%. The reference group proportion (deferred PrEP) of pre-term delivery pregnancy outcome as a main clinically-relevant adverse event is 0.185 or 18.5%.

Maternal Adverse Events (2% margin difference)

Other maternal adverse events will include abnormal chemistry (Grade \geq 2) results. As reported in the PROMISE study, Grade 2 or higher chemistry abnormalities were significantly higher in HIV infected pregnant women randomized to TDF containing ART (3%) compared to AZT/sdNVP (1%) (p<0.03).

Maternal and Infant Bone Mineral Density (4-7% margin difference)

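### Secondary HIV endpoint: the stated incidence rates give 10.0–10.5% versus about 5.0–5.25%, not 12.72% versus 6.36%; 346 per arm does not allow for 10% loss; and power at the planned 442 per arm is unstated and depends on which input was meant

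*Combined protocol and SAP*

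**What the plan says.** Section 10.3 (Secondary Endpoint) sizes a comparison of HIV infections between arms: a 50% reduction, 5% significance, 80% power and 66 infections in total. It divides them as "44 in control arm [cumulative incidence of 12.72%] and 22 in the intervention arm [cumulative incidence of 6.36" per cent. It then gives the source of the risks: "This assumes an HIV incidence of 3 per 100 person years during the 6 months of pregnancy and 6 per 100 person years during" a year and a half of breastfeeding, with a citation to reference 9. The sample size follows: "Based on these assumptions, we would require 334 subjects in group or 668 in total". The allowance for loss is: "Assuming a loss to follow-up of 10%, we would need to increase this to 346 women in each group".

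This calculation does not set enrolment. For the trial as a whole, section 10.3 says "we based our sample size on the expected preterm delivery proportion among HIV uninfected women", and from 421 per arm it concludes: "Assuming a loss to follow-up of 5%, we would need 442 women in each group". Section 10.4 names Fisher's exact test for the HIV comparison. No power for that comparison at 442 per arm appears in the protocol.

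**The concern.** The rates, cumulative incidences, sample size and loss-adjusted size are presented as one chain, each following from the one before. Two links fail: rates to risks, and 334 to 346. A reader therefore cannot tell what the 80% power claim rests on.

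The stake is limited, because HIV incidence is secondary and 442 exceeds 346. But section 10.3 powers a comparison and section 10.4 tests it. If 80% power is taken at face value and the stated rates are the true assumption, a non-significant HIV result would be given more weight than it deserves.

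**Working it through.** **Inputs.** Section 10.3: 3 per 100 PY for 0.5 years; 6 per 100 PY for 1.5 years; 50% reduction; α = 0.05; 80% power; 66 infections (44 and 22); 334, 346, 421 and 442 per arm; losses of 5% and 10%. Section 10.1: equal allocation. Section 10.4: Fisher's exact test. Sidedness is not stated for this endpoint; two-sided is used here because only that reproduces the plan's figures (see the objection).

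**1. The plan's own figures.**
- Events for a halved hazard: 4 × (1.960 + 0.842)² / (ln 2)² = 65.3, so 66. This matches.
- Pooled-Z sample size, n = [1.960·√(2p̄(1−p̄)) + 0.842·√(p₁(1−p₁) + p₂(1−p₂))]² / (p₁−p₂)², with p₁ = 0.1272 and p₂ = 0.0636: 333.7, so 334. This matches.
- 44/346 = 12.72% and 22/346 = 6.36%. The percentages are the event counts divided by the loss-adjusted size. At 334 per arm they give 334 × (0.1272 + 0.0636) = 63.7 infections, not 66.

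**2. Rates to risks.**
- Cumulative rate: 0.03 × 0.5 + 0.06 × 1.5 = 0.105.
- Control risk: 10.5% if read directly as a proportion, or 1 − exp(−0.105) = 9.97%.
- Intervention risk: 5.25% or 4.98% if the risk is halved; 1 − exp(−0.0525) = 5.11% if the rate is halved.
- A control risk of 12.72% needs a cumulative rate of −ln(1 − 0.1272) = 0.136, and 0.136/0.105 = 1.30, so 30% above the stated one.

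**3. Allowance for loss.**
- 334/0.9 = 371.1, so 372.
- By the convention that takes 421 to 442 (421 × 1.05 = 442.05): 334 × 1.10 = 367.4, so 368.
- 346 corresponds to 1 − 334/346 = 3.5% loss.

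**4. Consequences.** Powers are two-sided at 5%. The Fisher figures are exact. 398 is 442 × 0.90 and 421 is the evaluable number at 5% loss.

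| Control vs intervention | n per arm for 80% (Z) | Z power at 334 | Fisher at 398 | Fisher at 421 | Fisher at 442, no loss |
|---|---|---|---|---|---|
| 12.72% vs 6.36% (as printed) | 334 | 80.0% | 84.6% | 86.5% | 88.2% |
| 10.5% vs 5.25% | 413 (412.0 unrounded) | 71.3% | 75.9% | 78.1% | 80.2% |
| 9.97% vs 4.98% | 436 | 68.8% | 73.3% | 75.6% | 77.7% |
| 9.97% vs 5.11% | 464 | 66.2% | 70.5% | 72.8% | 75.0% |

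The last three rows are the stated rates under three conversions. Adjusted for 10% loss, their sizes run from 413/0.9 = 458.9 (459) to 464/0.9 = 515.6 (516). Expected infections at 398 per arm are 59–63 on the stated rates and 75.9 on the printed risks.

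**The case against.** **The percentages may be right and the rates wrong.** This stands. The 334 reproduces exactly from 12.72% versus 6.36%, so those risks fit the calculation that was run. In that case power at 442 per arm with 10% loss is about 85% and there is no shortfall. A reader might infer that the trial has only 70–76% power for HIV; the documents do not support that as an unconditional statement. Applying the 6 per 100 PY rate for two years after the six months of pregnancy would give 1 − exp(−0.135) = 12.63%, close to the printed figure, but the section says 18 months.

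**Excluding 10% of women is harsh.** This also stands. Section 10.4 includes all randomised women and section 7.20 tests for HIV at every visit, so a woman lost late contributes infections found earlier. With all 442 followed fully, Fisher power on the stated rates is 75–80%. The 70–76% range is therefore conservative, and its lower end also takes the least favourable conversion.

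**The test might be one-sided.** A one-sided 5% pooled Z can give 334 from the stated rates, at 10.24% versus 5.12% (1 − 0.97^0.5 × 0.94^1.5 = 10.24%). But one-sided calculation gives 52 events rather than 66, and 263 per arm from the printed risks rather than 334. The printed figures belong together only as two-sided.

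**The endpoint is secondary.** Section 2.3 words the objective as estimation, section 10.4 plans confidence intervals, and section 10.4 leaves full analysis details to a later SAP. This limits the consequence but does not remove the mismatch.

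**Two further inferences go too far.** Section 7.17 says "The target retention rate will be 90% per annum", with participation "up to 2 years for those who enroll early in pregnancy". That would be 1 − 0.9² = 19% loss over two full years, and one might call it a contradiction of the 5% and 10% figures. It is an operational goal, worth noting but not a sample-size error. Likewise, section 1.3 reports reference 9 as 4.7 per 100 PWY in pregnancy and 2.9 postpartum, not 3 and 6. That is a citation query. It does not show the rates to be wrong, since section 1.2 describes local postnatal seroconversion as higher than antenatal, the same direction as 3 and 6.

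**Conclusion.** The inconsistency is definite. On the rates given, the control risk is 10.0–10.5%, not 12.72%. The 80% power claimed at 334 per arm is then 66–71% (two-sided pooled Z), and 413–464 per arm would be needed before loss. The 346 does not contain a 10% allowance, whichever input is right.

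Power at 442 per arm for the planned test is missing. With 398 evaluable it is 70–76% if the rates stand and about 85% if 12.72% versus 6.36% stands. These figures assume a true 50% reduction, a two-sided 5% Fisher's exact test, and lost women contributing nothing. The practical effect is modest, because preterm delivery sets enrolment and the HIV endpoint is secondary, but the text should be corrected.

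**What to change.** Amend the Secondary Endpoint text in section 10.3, and carry the result into the later SAP:

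1. State which input was intended, the rates or the cumulative incidences, and make the two agree.
2. Delete 346, since 442 per arm governs. If it is kept, recompute it from the chosen input: 372 (or 368 by the convention behind 442) only if 12.72% versus 6.36% stands; about 459–516 after 10% loss if the rates stand. Changing 346 to 372 while keeping the rates would put another wrong number in the protocol.
3. Replace the 80% claim with two-sided Fisher's exact power at 442 per arm, naming the risks and the loss assumption. If the rates stand, for example: 10.0% versus 5.0%, 442 randomised per arm, 10% loss (398 evaluable), power about 73%. If the printed risks stand: about 85% on the same basis.
4. Check the citation of the rates to reference 9. A sensitivity row using 4.7 and 2.9 per 100 PWY is optional.

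The cost is wording only, with no change to enrolment, visits or the primary analysis. The downside is that the stated power for a secondary endpoint may become less favourable.
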